2.1.1 Handling Mis-randomization and Mis-stratification

There is no stratification factor in the randomization of this study. If a subject is misrandomized, i.e., taking the wrong medication as randomized, the subject will be analyzed as treated (using the treatment received) for the mITT and Safety populations, while excluded from analysis using the PP population.

2.2 Analysis Visit Windows

All days are referenced to day 1 (day of study medication treatment). Unless otherwise defined, baseline value is the last non-missing observation prior to treatment on day 1. Unless otherwise specified, visit windows are defined as below for mITT/Safety population for up to the end of the randomized period of the study, using study days relative to the day of study medication treatment for the randomized period of the study:

For the open-label period of the study, the visit windows are defined as in the table below. All the study days are relative to the day of study medication treatment for the open-label period of the study.

Unless otherwise stated, when multiple observations are captured in the same visit window, the observation closest to the target date of visit will be used for the window. If 2

observations are equidistant from the target date, then the latter observation will be used for the window. The only exception is for clinical laboratory variables, where the last nonmissing observation will be used. Because re-runs of laboratory variables may only involve one or a few variables, leaving the rest missing, this rule will be applied separately for each variable for non-missing data only.

A separate window for the PP population would not be generated as the population is only used to analyze IELT data, which is not window-based.

2.3 Data Conventions

- A one-sided, alpha=0.1 significance level will be used for this study for treatment comparisons, i.e., treatment differences are considered significant if the 1-sided p-value of the test used in the comparison is less than or equal to 0.1.
- Data will be pooled across centers in all analyses. Placebo patients from different cohorts will also be pooled to form the placebo treatment group in all analyses.
- Day 1 is defined as the day of the first study medication administration. Study day is calculated as: Study day=visit date-day 1 date +1 for visits occurred after day 1 and study=visit date -day 1 date for visits occurred before day 1.
- The Medical Dictionary for Regulatory Activities (MedDRA) will be used to code all adverse events and medical history.
- Medications will be coded by the World Health Organization Drug Dictionary Enhanced (WHO DDE) preferred name for the medication's name and MedDRA for the medication's indication.
- All adverse events/medications with missing onset/stop dates will be identified and the missing dates will be imputed as follows:
 - a) For adverse event onset date: if day and month are missing but year is available then the imputed date would be January 1st of that year, or day 1 if they are in the same year. If day is missing but month and year are available then the imputed day will be the first day of the month or day 1 if they are in the same month and year.
 - b) For adverse event stop date: if day and month are missing but year is available then the imputed day will be December 31st of that year, or the study exit date if they are in the same year. If only day is missing but moth and year are available then the imputed day will be the last day of the month of the year, or the study exit date if they are in the same month and year.

- Data from unscheduled/re-test visits, excluding lab data, will also be treated the same way as scheduled visits, i.e., put in the visit window and decided by the visit day's distance to target day as which one to be used in the analyses.
- Weight and height will be presented with the metric system units and laboratory data will be presented with the Standard International (SI) units.
- Summary statistics for continuous/ordinal data include sample size (N), mean, standard deviation, minimum, median, and maximum and that for categorical data include sample size (N), frequency count and percentage.
- Change from baseline is calculated as follow-up minus baseline, and treatment difference will be calculated as BOTOX[®] minus placebo.
- The type III sums of squares will be used for all analysis of covariance (ANCOVA) and analysis of variance (ANOVA) models.
- Unless otherwise specified, comparisons on categorical data will be performed using Pearson's Chi-square test. When 25% or more of the cells have expected counts of less 5, Fisher's exact test will be used.
- Except for AE and medication onset/stop dates, missing data will not be imputed.

3. Disposition and Exit Status

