7.3 Hypothesis and Methods of Analysis

7.3.1 Primary Efficacy Analyses

The primary timepoint for analysis is week 12.

The primary null hypothesis: At the primary efficacy timepoint the difference in mean change from baseline in logarithm value of the geometric mean IELT between placebo and BOTOX is at zero; and there is no dose response shown in the change from baseline in logarithm value of the geometric mean IELT.

The primary alternative hypothesis: At the primary efficacy timepoint the difference in mean change from baseline in logarithm value of the geometric mean IELT between placebo and BOTOX is not equal to zero; or there is a dose-response in the change from baseline in logarithm value of the geometric mean IELT.

The primary efficacy variable (change from baseline in the logarithm value of individual patient's geometric mean IELT) in relation to dose levels will be analyzed using an analysis of covariance (ANCOVA) model with treatment as the fixed effect and baseline logarithm value in geometric mean IELT as the covariate to assess the relationship of response across the BOTOX dose levels. Geometric means of the IELT up to week 12 will be log-transformed prior to analysis.

No multiplicity adjustment will be taken.

Analysis of the primary efficacy variable using a PP population will also be performed.

The log-transformed primary efficacy variable will also be analyzed with a linear regression model to assess the dose-response of the active treatments.

Details will be specified in the statistical analysis plan.

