5.4 Other Analyses of Secondary Efficacy Variables

Nonparametric analysis using the Wilcoxon rank-sum test will be performed on the geometric mean IELT up to weeks 2, 4, 6, 8 and 10 as well as interval-based geometric mean IELT for weeks 4, 8 and 12, to compare each active BOTOX[®] dose level vs. placebo. Responder analyses described in 5.2.2 will also be carried out for geometric mean IELTs up to weeks 2, 4, 6, 8 and 10.

Treatment comparisons of each active BOTOX[®] dose level vs. placebo Geometric mean IELT up to weeks 4, 8 and 12 will also be performed using methods described in Zhou et al, 1997:

1. The likelihood-based Z-score test: the comparison between an active BOTOX[®] dose level *i* and placebo is evaluated by the statistic Z_i :

$$Z_{i} = \frac{\hat{\mu}_{i} - \hat{\mu}_{0} + \frac{1}{2}(S_{i}^{2} - S_{0}^{2})}{\sqrt{\frac{S_{i}^{2}}{n_{i}} + \frac{S_{0}^{2}}{n_{0}} + \frac{1}{2}(\frac{S_{i}^{4}}{n_{i} - 1} + \frac{S_{0}^{4}}{n_{0} - 1})}}$$

Where $\hat{\mu}_i$ and $\hat{\mu}_0$ are the sample mean of the log-transformed geometric mean IELT of dose level *i* and placebo, S_i^2 and S_0^2 are the sample variance of the log-transformed geometric mean IELT of dose level *i* and placebo, and n_i and n_0 are the sample size of dose level *i* and placebo, respectively.

Assuming that for each of the active dose level *i* and placebo, the geometric mean IELT are independently log-normally distributed with means M_i and M_0 , respectively, then Z_i tests the null hypothesis of $M_i=M_0$, and under the null hypothesis Z_i is approximately standard normal.

2. Bootstrap approach:

Let \overline{T}_i , \overline{T}_0 and $\overline{T}^{(i,0)}$ be the sample mean of the geometric mean IELT of the dose level i, placebo and the two groups combined, respectively. $T_k^{(i)} = T_{ik} - \overline{T}_i + \overline{T}^{(i,0)}$ and $T_j^{(0)} = T_{0j} - \overline{T}_0 + \overline{T}^{(i,0)}$ form a sample with common mean $\overline{T}^{(i,0)}$, where T_{ik} and T_{0j} are the geometric mean IELT for the kth patient in dose level i and the jth patient in the placebo group, for k=1, ..., n_i and j=1,..., n_0. Resample from them with replacement 2000 times, $Z_{i1}^{*(b)}$,..., $Z_{in_i}^{*(b)}$ and $Z_{01}^{*(b)}$,..., $Z_{0n_0}^{*(b)}$ for each b=1, ..., 2000. Compute

$$t_{b,i}^* = \frac{\overline{Z}_i^{*(b)} - \overline{Z}_0^{*(b)}}{\sqrt{\frac{\tau_i^{*(b)2}}{n_i} + \frac{\tau_0^{*(b)2}}{n_0}}}, \text{ for b=1,..., 2000.}$$

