Where $\overline{Z}_i^{*(b)}$, $\tau_i^{*(b)2}$, $\overline{Z}_0^{*(b)}$, and $\tau_0^{*(b)2}$ are the sample mean and variance for the active does level *i* and placebo for the bth resample, respectively. The test statistic,

$$t_{obs,i} = \frac{\overline{T_i} - \overline{T_0}}{\sqrt{\frac{\hat{\tau}_i^2}{n_i} + \frac{\hat{\tau}_0^2}{n_0}}}$$

Where $\hat{\tau}_i^2$ and $\hat{\tau}_0^2$ are the sample variances of the observed geometric mean IELT of active dose level *i* and placebo, respectively.

Then the achieved significance level (ASL) for testing $H_0: M_i=M_0$ vs. $H_a: M_i \neq M_0$, for the dose level *i*, where M_i and M_0 are the means of the IELTs of dose level *i* and the placebo under the log-normal distribution, respectively.

$$\hat{ASL}_{i} = \frac{\# of \ times \mid t_{b,i}^{*} \mid \geq \mid t_{obx,i} \mid}{2000}$$

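### SAP 5.4 defines the bootstrap significance level only as a two-tailed count, while SAP 2.3 judges treatment comparisons by a one-sided p-value of at most 0.1

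*SAP*

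**What the plan says.** SAP 2.3 sets a one-sided level of 0.1 for treatment comparisons and gives the operative rule: "treatment differences are considered significant if the 1-sided p-value of the test used in the comparison is less than or equal to 0.1". The same section fixes the sign ("treatment difference will be calculated as BOTOX" minus placebo) and the comparator: "Placebo patients from different cohorts will also be pooled to form the placebo treatment group in all analyses". Protocol 7.5 computes power at one-sided 0.10, and the clinical hypothesis in Protocol 2.2 is that IELT increases.

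SAP 5.4 adds two tests of each dose against placebo for the geometric mean IELT up to weeks 4, 8 and 12. The first is a signed Z-score, which under the null "is approximately standard normal". The second is a bootstrap. Both groups are shifted to a common mean, then "Resample from them with replacement 2000 times", and a studentised difference t* is computed for each resample. The result is introduced by "Then the achieved significance level (ASL) for testing" M_i = M_0 against M_i ≠ M_0. It is defined as the number of resamples with |t*| ≥ |t_obs|, divided by 2000. SAP 5.4 gives no cut-off for the ASL, no halving rule and no directional version.

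**The concern.** The bootstrap is a treatment comparison, so the SAP 2.3 rule covers it and asks for a one-sided p-value. The printed formula produces a two-tailed one. An analyst could compare the ASL with 0.10, halve it and check the sign, or count one tail only. These give different answers on the same data.

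The bootstrap will be reported beside the Z-score test, which gives a one-sided p-value directly. If the two tests use different tails, a reader may take a non-significant bootstrap as failing to confirm a dose, when much of the disagreement comes from how the p-value was defined.

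**Working it through.** **Design level.** Table 7-1 was recomputed as a two-sample t-test on the log scale with δ = ln(fold), σ = √ln(1 + CV²) and n₁ + n₂ − 2 degrees of freedom. For 12 vs 12, 2-fold, CV 1:
- σ = √ln 2 = 0.833
- noncentrality = 0.693 / (0.833 × √(1/12 + 1/12)) = 2.04
- critical t (22 df, one-sided 0.10) = 1.321
- power = 76.4%, against 76% printed

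All 27 cells reproduce within 2 points at one-sided 0.10. At two-sided 0.10, 26 of the 27 do not (63.0% for the cell above). One-sided 0.10 is therefore the level the design works at.

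**Inputs for the bootstrap.** Planned placebo after pooling is 5 × 2 + 12 = 22. BOTOX groups are 8 (Cohorts 1-5) or 12 (Cohort 6). CVs of 1 and 1.5 come from Table 7-1 (σ = 0.833 and √ln 3.25 = 1.086); the source studies range from 0.85 to 1.64. Patient geometric means are taken as log-normal with equal CV in both groups. The SAP 5.4 procedure was simulated with 2000 resamples and 10,000 trials per scenario (Monte Carlo standard error at most 0.5 point). Because the resampling sentence can be read as drawing within each shifted group or from the two combined, both were run.

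**Detection of a 2-fold effect**

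| Resampling | Groups | CV | ASL ≤ 0.10 | ASL/2 ≤ 0.10 and t_obs > 0 | #(t* ≥ t_obs)/2000 ≤ 0.10 |
|---|---|---|---|---|---|
| Within | 12 v 22 | 1 | 42.4% | 65.8% | 79.9% |
| Within | 12 v 22 | 1.5 | 20.2% | 41.7% | 62.6% |
| Within | 8 v 22 | 1 | 27.0% | 50.6% | 70.6% |
| Within | 8 v 22 | 1.5 | 11.6% | 28.9% | 52.9% |
| Combined | 12 v 22 | 1 | 56.4% | 73.6% | 79.5% |
| Combined | 12 v 22 | 1.5 | 30.8% | 49.2% | 58.0% |
| Combined | 8 v 22 | 1 | 38.5% | 59.1% | 71.3% |
| Combined | 8 v 22 | 1.5 | 18.5% | 35.9% | 50.7% |

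For comparison, the Z-score test at one-sided 0.10 detects 76.6% (CV 1) and 54.8% (CV 1.5) at 12 v 22.

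**Splitting the gap, 12 v 22, CV 1.** Within group: 79.9 − 42.4 = 37.5 points. Halving recovers 65.8 − 42.4 = 23.4, and 14.1 remain. Combined: 79.5 − 56.4 = 23.1 points. Halving recovers 17.2, and 5.9 remain. The remainder is there because the bootstrap t is skewed when log-normal groups are small and unequal.

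**No effect.** The share favouring BOTOX is all ASL ≤ 0.10 flags minus those with t_obs < 0.

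| Resampling | Groups | CV | ASL ≤ 0.10, all | of which BOTOX lower | favouring BOTOX | one-sided count ≤ 0.10 |
|---|---|---|---|---|---|---|
| Within | 12 v 22 | 1 | 8.0% | 6.0% | 2.0% | 11.0% |
| Within | 12 v 22 | 1.5 | 7.1% | 5.6% | 1.5% | 12.0% |
| Within | 8 v 22 | 1 | 9.6% | 8.2% | 1.4% | 9.8% |
| Within | 8 v 22 | 1.5 | 8.6% | 7.7% | 0.9% | 10.3% |
| Combined | 12 v 22 | 1 | 10.1% | 7.2% | 2.9% | 9.7% |
| Combined | 12 v 22 | 1.5 | 10.1% | 7.6% | 2.5% | 9.5% |
| Combined | 8 v 22 | 1 | 10.0% | 8.3% | 1.7% | 8.7% |
| Combined | 8 v 22 | 1.5 | 10.2% | 8.9% | 1.3% | 8.5% |

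At 12 v 12, CV 1, the ASL flags split evenly (3.4 and 3.1 points within group; 5.1 and 5.2 combined). The tilt against BOTOX thus comes from unequal group sizes with skewed data. The one-sided count there flags 13.2% (within) and 10.5% (combined).

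**Larger effects, 12 v 22, CV 1.** In smaller runs (2,000 to 3,000 trials), a 3-fold effect gives 72% for ASL ≤ 0.10 against 97% for the one-sided count within group, and 89% against 97.5% combined. At 4-fold the gap is about 20 points within group and 3 combined.

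**The case against.** The strongest reply is that SAP 2.3 already settles the matter: it asks for the one-sided p-value of whichever test is used, it fixes the sign, and the signed t* values exist. A careful analyst would count #(t* ≥ t_obs) without being told. That stands in part. A reader might infer that the rule cannot be applied to the bootstrap at all, and the documents do not support that, since the same resamples supply the one-sided p-value. What remains is that SAP 5.4 prints a different formula and a different alternative, and a programmer following it will not produce what SAP 2.3 needs.

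Second, nothing in the SAP says to hold the two-tailed ASL to 0.10. This is correct. The power gap is conditional on that reading and should not be reported as a loss the plan prescribes. The gap also shrinks with larger effects under combined resampling, and part of it is skewness rather than sidedness.

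Third, a reader might extend the point to the primary analysis, because Protocol 7.3.1 states its alternative as a difference that "between placebo and BOTOX is not equal to zero" and SAP section 12 lists no deviation. The documents do not carry that. Protocol 7.3.1 sets no alpha and defers ("Details will be specified in the statistical analysis plan"), Protocol 7.5 already uses one-sided 0.10, and SAP 2.3 implements it. Rewording those sections would be drafting preference.

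**Conclusion.** Wrong as written, minor. The mismatch between the SAP 2.3 rule and the SAP 5.4 formula is on the page and does not depend on simulation. Its size does. The figures assume a 0.10 cut-off borrowed from SAP 2.3, log-normal data with equal CVs, Cohorts 1-5 run as planned, and Cohort 6 as a dose group of its own (the doses are blacked out). On that basis the printed ASL is far stricter than the study rule when BOTOX works, and with no effect most of its flags point to BOTOX being lower.

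A reader might also infer that SAP 5.4 should require within-group resampling. The calculations do not support that instruction: at the planned sizes the one-sided count's null rate is 9.8-12.0% within group and 8.5-9.7% combined. The choice of scheme is a separate question.

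The consequence is limited. The bootstrap is one of several supportive analyses in an exploratory pilot without multiplicity adjustment, and no dose or stopping decision in these documents rests on it.

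**What to change.** In SAP 5.4, change the bootstrap alternative to M_i > M_0 and define ASL = #(t* ≥ t_obs)/2000, judged at the 0.10 level of SAP 2.3. No other section needs to change for this point.

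The cost is a sentence in the SAP and one line of code, before database lock. There are two downsides. The test would give no formal signal if BOTOX shortened IELT. The one-sided count is also not exactly calibrated: its null rate runs from about 8.5% to 12% at the planned group sizes, and reaches about 13% at 12 v 12 with within-group resampling.

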8.2 Washout of Prohibited Medications

If washout is required for the purposes of this study then the patient must sign the informed consent before the washout is commenced.

Patients taking prohibited medications must undergo a washout of the medications for at least 28 days prior to performing screening efficacy assessments (eg, stopwatch IELT measurements, SID, and health outcomes questionnaires). Any screening IELT data collected

prior to washout completion will not be considered as evaluable. The screening period may occur over several visits if needed.

A full list of prohibited medications requiring washout is provided in Section 4.5.2.

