4.2 Disease Characteristics

Baseline disease characteristics include baseline IELT,

Summary statistics will be provided for each variable by treatment group as well as overall. An one-way ANOVA will be used to compare these characteristics among treatment groups. For IELT, as the eligibility is based on the average of the latest four eligible events collected at during screening period, arithmetic mean will be used.

4.3 **Prior Medications**

Prior medications are medications captured in the CRF that are taken prior to the day 1. A medication is a prior medication if the (imputed) onset date is before day 1. The number and percent of patients who had taken prior medications will be presented for each treatment group and overall by the WHO DDE preferred name and the MedDRA preferred term (PT) of the medication's indication.

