4.4 Concomitant Medications/Procedures

Concomitant medications are medications taken on or after the day of study medication administration. A medication is a concomitant medication if the (imputed) onset date is on or after day 1, or if the onset date is before day 1 and the stop date is after day 1 (discontinued after day 1 or ongoing during the study).

The number and percent of patients who had taken concomitant medications will be presented for each treatment group and overall by the WHO DDE preferred name and the MedDRA PT of the medication's indication.

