6.4 Adverse Events

AEs will be coded from the verbatim text into PT and the primary SOC using MedDRA.

AEs are collected both for the screening/baseline period pretreatment (which are referred to as pretreatment AEs) and for the follow-up period after treatment is initiated (which are referred to as posttreatment AEs). A treatment-emergent adverse event (TEAE) is an adverse event with onset on or after the initiation of study treatment or an adverse event with onset prior to study treatment that worsened in severity or became serious after the initiation of study treatment. For the randomized period of the study, TEAEs are those with onset on or after the first study treatment, and prior to the study treatment for the open-label period, if applicable; for the open-label period, TEAEs are those with onset on or after the study treatment for the open-label period.

Three incidence rate tables are standard for summarizing all TEAEs:

- by descending order of incidence rate
- by primary SOC and PT
- by primary SOC, PT and severity

Number and percent of patients with TEAEs will be tabulated by relationship to study drug and study procedures. All treatment-related TEAEs, either study drug-related or study procedure-related will also be presented by descending incidence and by primary SOC and PT for each treatment group. Separate tables will be generated for study drug-related and study procedure-related TEAEs. TEAEs leading to study discontinuation will also be tabulated by primary SOC and PT for each treatment group.

No statistical comparisons will be made for any adverse event table.

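### SAP 2.3 imputes a partial AE onset in the Day-1 month or year to Day 1 without checking the stop date, so an event known to have ended before injection becomes treatment-emergent

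*SAP*

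**What the plan says.** SAP 2.3 introduces its date rules for both record types: "All adverse events/medications with missing onset/stop dates will be identified and the missing dates will be imputed as follows". The two rules that follow are worded for adverse events only: a) for onset and b) for stop.

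Under a), an onset with day and month missing becomes "January 1st of that year, or day 1 if they are in the same year". With only the day missing, "the imputed day will be the first day of the month or day 1 if they are in the same month and year". The reference date is fixed: "Day 1 is defined as the day of the first study medication administration". No condition on the stop date is attached.

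The classifications rest on onset:

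- SAP 6.2: an AE is pretreatment if its onset is before Day 1 of the randomized period.
- SAP 6.4: a treatment-emergent AE is first an "adverse event with onset on or after the initiation of study treatment". The alternative limb covers earlier events that worsen or become serious after treatment.
- SAP 4.3: a "medication is a prior medication if the (imputed) onset date is before day 1".
- SAP 4.4: a "medication is a concomitant medication if the (imputed) onset date is on or after day 1". A second branch does check the stop date, but only for onsets before Day 1.

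Pre-injection records will exist. Protocol 9.1.1 collects AEs from informed consent. Protocol 8.2 requires a washout: "Patients taking prohibited medications must undergo a washout of the medications for at least 28 days prior to performing screening efficacy assessments". Protocol 4.5.3 stops anticoagulants, antiplatelets and NSAIDs at least 3 days before treatment.

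**The concern.** Setting an uncertain onset to Day 1 is a sensible caution when the event may have run into the post-injection period. When the stop date is known to be earlier than Day 1 there is nothing left to be cautious about. The rule then yields an impossible record, with onset after stop, and the downstream definitions move it to the post-injection side.

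Safety is half of the study's stated objective, so the TEAE tables are main outputs. An event that was over before any injection would appear in the treatment-emergent incidence of BOTOX or placebo and be missing from the pretreatment table. If drugs follow the same rule, a medication stopped as the protocol required could be shown as used on or after injection and be missing from the prior-medication table. That would contradict the opening definitions in SAP 4.3 and 4.4, which go by when the drug was actually taken.

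**Working it through.** The plan states no figure for this point. The check is to apply the printed rules to constructed records.

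**1. Rules as coded**

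- Onset, year only: Day 1 if the year is that of Day 1, otherwise 1 January.
- Onset, month and year: Day 1 if both match Day 1, otherwise the first of the month.
- AE: treatment-emergent if onset ≥ Day 1, otherwise pretreatment.
- Drug: prior if onset < Day 1; concomitant if onset ≥ Day 1, or if onset < Day 1 and stop > Day 1.

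**2. Test records** (assumed Day 1 = 20 Sep 2016; drug rows assume that rule a) covers medications)

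| Record | Known onset | Known stop | Imputed onset | Days after own stop | Class as written | Class with stop-date condition |
|---|---|---|---|---|---|---|
| Screening AE | Sep 2016 | 12 Sep | 20 Sep | 8 | TEAE | pretreatment |
| Screening AE | 2016 | 25 Aug | 20 Sep | 26 | TEAE | pretreatment |
| Washed-out drug | 2016 | 15 Jul | 20 Sep | 67 | concomitant only | prior only |
| NSAID | Sep 2016 | 10 Sep | 20 Sep | 10 | concomitant only | prior only |
| Drug (control) | 2015 | 15 Jul 2016 | 1 Jan 2015 | n/a | prior only | unchanged |
| Drug (control) | Jun 2016 | 15 Jul 2016 | 1 Jun 2016 | n/a | prior only | unchanged |

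All four records with a partial onset in the Day-1 month or year and a stop before Day 1 are misclassified. The condition corrects all four and leaves the controls alone.

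**3. Which drugs can be reached**

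Take every Day 1 in an assumed calendar year (2016, 366 dates) and count how often the last dose falls in the same month or year as Day 1.

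- Gap of 29 days (just past a 28-day washout): same month on 18/366 = 4.9% of dates, same year on 92%.
- Gap of 42 days or more: same month on 0 dates. At 70 days, same year on 81%.
- Gap of 4 days (just past the 3-day stop): same month on 318/366 = 87%.

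These are calendar shares with Day 1 uniform over the year. They are upper bounds because onset precedes the last dose. So washed-out drugs are exposed almost only through the year-only branch. The month branch matters for screening AEs and for drugs stopped shortly before treatment.

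**4. Weight of one record**

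- BOTOX dose group in Cohorts 1-5: 1/8 = 12.5 percentage points.
- BOTOX in Cohort 6: 1/12 = 8.3 points.
- Placebo pooled across cohorts (SAP 2.3): 5 × 2 + 12 = 22 planned, and 1/22 = 4.5 points.

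**The case against.** **The medication half is inferred.** Rules a) and b) name adverse events only. This stands. Three places suggest that the same rule was meant for drugs: the lead-in in SAP 2.3, the statement at the end of that section that medication dates are among the few items imputed, and the reference to an imputed onset in SAP 4.3 and 4.4. None prints the rule. If it does not apply, medications have no stated rule. The AE half does not depend on this.

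**Screening events are already called pretreatment.** SAP 6.4 uses that label for AEs collected before treatment. It is a general description and does not override the onset-based TEAE definition in the same section. It is true that SAP 6.2 and 6.4 do not say imputed when they refer to AE onset, but SAP 2.3 gives the imputed AE date no other use.

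**The branch shares look large.** A reader might note that a mean of about 14.7 days of the month precede Day 1. For AE onsets spread evenly over a 42-day (70-day) screening period, 14.7/42 = 35% (14.7/70 = 21%) then fall in the Day-1 month. Some 94% (90%) fall in the Day-1 year. It is tempting to infer error rates of that size. The documents do not support that. These are shares of partial-date records sent to Day 1, and for many of them Day 1 is the cautious choice. An error also needs a known stop before Day 1. Since AEs are asked about at every visit, onsets with the month unknown should be uncommon.

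**The consequences are descriptive.** This stands. SAP 6.4 makes no statistical comparison of AEs, and medications are only tabulated. Relationship to drug or procedure is judged separately, so an event over before injection should not reach the treatment-related tables.

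**Conclusion.** For adverse events the plan is wrong as written. A partial onset in the Day-1 month or year combined with a known stop before Day 1 always produces an onset after the stop and a false TEAE, and no other section catches it. For medications the same error follows if rule a) is applied to them, as the SAP suggests. If it is not, the medication rule is missing.

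The size per record is 12.5, 8.3 or about 4.5 percentage points, depending on the group. How many such records will occur is unknown, because the documents give no frequency of partial dates.

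Two stronger readings do not hold. A reader might infer that drugs stopped for the 28-day washout will generally be listed as concomitant. The month branch reaches them on at most 4.9% of Day-1 dates, and a drug started in an earlier year is classified correctly. A reader might also infer that the efficacy results or the per-protocol set are affected. The IELT analysis does not use these dates, and per-protocol exclusion rests on protocol deviations. The effect is confined to the pretreatment AE, TEAE, prior-medication and concomitant-medication tables.

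**What to change.** In SAP 2.3, impute a partial onset to Day 1 only if the stop date is missing, ongoing, or on or after Day 1. Otherwise impute the earliest date consistent with the known part (first of the month, or 1 January), never later than the stop date and, for AEs, not before informed consent. A partial stop date can be compared after rule b) has been applied to it.

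The consent floor is needed. AEs are collected only from consent, and SAP 4.5 defines medical history by onset before consent. With Day 1 on 20 Sep 2016 and the normal maximum of 42 + 28 = 70 days of screening, consent would fall no earlier than 12 Jul 2016, so an onset of 1 January would precede it.

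In SAP 4.4 and 6.4, state that a record with a stop date before Day 1 is neither concomitant nor treatment-emergent. In SAP 2.3, state explicitly that the onset and stop rules cover medications as well as AEs.

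The cost is a few sentences in the SAP and a small programming change before database lock, with no new data.
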